Times to obtain Blood Specimens and other Samples and Studies (Flow Charts 3-4, Gantt Chart, pages 17, 26 and 27, below). After providing their informed consent to participate, subjects will be asked to provide 2 tubes of blood for chemistry and hematology testing. Beginning at the time of dosing, participants will also be asked to provide serial blood samples for AQ-13 drug and metabolite blood levels 8, 7 and 7 times on days 1-3, once on days 4 and 5, twice in week 2 (at each of the twice-weekly outpatient visits) and once per week in weeks 3-6 (days 15-42). This information is provided in tabular form and graphically in a Gantt Chart below in Section 7 (page 27). To facilitate the drawing of multiple blood specimens, a heparin lock plastic catheter with a scalp vein needle will be placed in the arm of participants for use during inpatient days 1-4 or 1-5.

Methods for Collecting Blood Specimens. Blood specimens will be obtained by finger stick or through the heparin lock plastic catheter for the screening blood smear, filter paper blot, and Hb, AQ-13 and AQ-13 metabolite levels. Subsequently, they will be obtained by venipuncture for the AQ-13 drug and metabolite levels and for the repeat chemistry and hematology panels beginning on day 4 of the inpatient stay or at the start of outpatient studies in Week 2. A heparin lock (scalp vein attached to a plastic catheter containing heparin to keep the line open) will be placed on inpatient day 1 to permit drawing 24-26 blood samples on inpatient days 1-4 or 1-5 without separate venipunctures for each sample.

Collection of Urine Specimens. To monitor the urinary excretion of AQ-13 and its two major metabolites, subjects will be asked to save their 24 hour urines during inpatient days 1-4.

Expected Duration of Subject Participation from the time of screening and enrollment to the conclusion of their participation in the study is 42 days (6 weeks).

Description of Subject Participation. As noted above, these subjects will be asked to provide or have:

- 32 Tubes of blood for a total volume of 160 ml (5 ml per tube),
- 4 (24 hour) urine collections on inpatient days 1-4,
- 7 Holter recordings at the times of screening (1 hour), during inpatient days 1-4 (24 hours each) and at the 1 and 2 week outpatient follow-up visit (2 hours),
- 2 Eye examinations at the times of screening and the 1 week outpatient follow-up visit.

[figure not shown]

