6.2.2 Special Assays or Procedures

Prior to treatment with AQ-13 or Coartem, subjects will have a 1 hour baseline Holter recording to exclude pre-existing arrhythmias and other cardiac abnormalities and a baseline eye examination to ensure that there are no pre-existing ocular abnormalities before treatment or any new ocular abnormalities (potential AEs) after treatment. Randomization will be performed after the chemistry, hematology, eye and Holter recording results have been checked to ensure there are no criteria for exclusion and that informed consent to participate has been obtained and signed. Special assays or procedures that will be used in these studies include:

- PCR testing for parasite genotypes and for the K76T point mutation in *pfCRT* (Mali; SOP),
- Fluorescence HPLC assay for AQ-13 and its metabolites (New Orleans; SOP),
- Holter recordings for evidence of arrhythmias (Mali and New Orleans; SOP),
- Eye examinations pre- and post-treatment to test for evidence of keratopathy, retinopathy, other pre-existing abnormalities or treatment-related ocular side effects (adverse events) (Mali; SOP),
- Pharmacokinetic analysis of AQ-13 drug and metabolite blood and urine levels (Mali and New Orleans; SOPs for AQ-13 HPLC, CRFs for Out-Patient Follow-Up).

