6.5 Inpatient Period

Blood samples will be taken for drug and metabolite levels on days 1-5 and hematology and chemistry panels on day 4. After screening Holter recordings have been obtained and reviewed for pre-existing arrhythmias, continuous 24 hour Holter recordings will be performed on each of days 1-4 (focusing on the time between 2 and 6 hours after dosing for maximal effects on the QT interval). Urine collections will be performed on each of days 1-4. An eye exam plus an additional 1 hour Holter recording will be performed at the end of week 1.

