6.6 Follow-up and Final Visits, if applicable

After completion of the 5-7 day inpatient stay (Flow Chart 4 below, and Table 1, above), there are 2 follow-up outpatient visits each week for the next 5 weeks (total of 6 weeks active involvement in the study). At each of the follow-up visits during Weeks 3-6, a blood sample is obtained for AQ-13 drug and metabolite blood levels to define the pharmacokinetics of AQ-13 and its metabolites. In addition, there is a final 1 hour Holter recording at the 2 week follow-up visit plus an in-depth interview about potential AEs.

Sequence of Events during the Follow-Up Outpatient Visits. The twice-weekly follow-up outpatient visits will include (in sequence): an interval history with discussion of potential AEs related to study drugs, review of current medications and a physical examination with recorded results for vital signs (blood pressure, heart rate, respiratory rate, temperature), conjunctival pallor, pulmonary, cardiac and abdominal examinations (including splenomegaly) (see the Out-Patient Follow-Up CRFs).

Allowable Windows (Times) for Follow-Up Outpatient Visits. The major purposes of the follow-up outpatient visits are to: 1] follow the pharmacokinetics of AQ-13 and its metabolites over time to estimate the terminal elimination $t_{1/2}$ and other pharmacokinetic parameters for AQ-13 and its metabolites in subjects with uncomplicated malaria and 2] to test for recurrent infection by distinguishing new infections (which do not represent recurrences or treatment failures) from recrudescences of infection with the same parasite genotypes (which do potentially represent treatment failures). Although the best data (in terms of points on the time-concentration curve to estimate the pharmacokinetic parameters) are provided by twice-weekly follow-up blood samples during the first two weeks (Weeks 1 and 2), the software that will be used for this purpose (PharSight) can adjust and still provide reasonable estimates of the relevant pharmacokinetic parameters no matter what the time points are. For this reason and because recurrent infection should be detected as soon as possible, late return visits will be permitted up to the final 6 week (42 day) time point.

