Coartem X ₄ =4 tabs			X ₄						X ₄		X ₄							X ₄	X ₄						X ₄			

X1 – To be performed by study Co-Investigator while inpatient and at follow-up

X2 – To be done over 96 hours (4 days), beginning at zero time on day 1

X3 – AQ-13 dose; to be given in the morning x 3 days.

X4 – Coartem dose (4 tablets in morning and afternoon x 3 days).

½ wks – at the end of week 1 and the end of week 2

* - blood draws at 96 and 120 hours after this, then twice a week for 6 weeks.

** - Holter recording for 1 hour at 1 and 2 week follow up visits.

Table 3.

WEEK ONE BLOOD SAMPLING SCHEDULE FOR AQ-13 DRUG AND METABOLITE LEVELS

Days	Day 1								Day 2								Day 3								4	5	6	
Hours	0	0.5	1	2	4	6	12	18	24	24.5	25	26	28	30	36	48	48.5	49	50	52	54	60	72	96	120			

Gantt Chart**ORGANIZATION OF THE PHASE 2 PROOF OF CONCEPT STUDY OF AQ-13**

	OUTPT	INPT	INPATIENT WEEK 1							OUTPATIENT FOLLOW-UP (WEEKS 2 TO 6)					
Recruitment	X	TESTS													
Informed Consent	X														
Thick Smear	X		X	X	X	X	X	X	X	2 per Week	2 per Week	2 per Week	2 per Week	2 per Week	2 per Week
Thin Smear	X														
Filter Paper Blot	X		X	X	X	X	X	X	X	2 per Week	2 per Week	2 per Week	2 per Week	2 per Week	2 per Week
Physical Exam	X		X	X	X	X	X	X	X	2 per Week	2 per Week	2 per Week	2 per Week	2 per Week	2 per Week
Hb	X						X								
Transport Decision	X														
Hematology Panel			X				X								
Chemistry Panel	X						X								
Eye Examination	X								X						
Holter (1 hour)	X								X	Day 14					
Holter (24 hours)			X	X	X	X									
Randomisation	X														
Drug Treatment			X	X	X										
Pharmacokinetics			8	6	7	1	1	1		2 per Week	1 per Week	1 per Week	1 per Week	1 per Week	
Parasite Clearance									X						
End of Inpatient Stay									X						
Completion of Study															Day 42
	OUTPT	INPT	INPATIENT WEEK ONE							OUTPATIENT FOLLOW-UP (WEEKS 2 TO 6)					
	TESTS	TESTS	1	2	3	4	5	6	7	8 to 14	15 to 21	22 to 28	29 to 35	36 to 42	
	DAYS									2	3	4	5	6	
	WEEK														

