7.1.2 Secondary Outcome Measures

- 1] Adverse Events (AEs) – within 4 weeks of treatment as judged by **blinded** physician reviewers to be possibly related to the study drug(s) using the same criteria as in the Phase 1 study.
- 2] Parasite clearance time – from the initiation of treatment to the first of 2 successive negative smears.
- 3] Time to recrudescence or reinfection – time from the initiation of treatment to the reappearance of asexual *P. falciparum* parasites on the thick smear.
- 4] Effects on the QT (QTc) interval – mean changes from the baseline pre-treatment QT (QTc) interval to the post-treatment QT (QTc) interval after treatment with AQ-13 or Coartem.
- 5] Pharmacokinetic parameters for AQ-13 – these will include measurements of AQ-13 blood levels over time (peak levels, AUC, MRT), drug distribution (Vd/F) and drug elimination ($t\frac{1}{2}$, Cl/F).
- 6] Fever clearance time: Time in hours from the initiation of therapy until disappearance of fever for at least 24 hours.

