Times to recrudescence and reinfection will be analyzed using life tables, and compared using the log rank test. Cox regression will be used to compare multiple (multivariate) predictors of times to recrudescence and reinfection. Pharmacokinetic parameters will be examined for AQ-13 doses and compared to data from the Phase 1 studies, as appropriate. **Using the same protocol as in the Phase 1 study [11], the relatedness of adverse events (AEs) to study drugs will be classified independently by two blinded physicians according to the definitions in section 8.3 on page 30 as unknown, not related, unlikely to be related, or possibly, probably or definitely related to the study drugs, based on temporal relationships and biological plausibility.** The frequencies of AEs will be compared between AQ-13 and Coartem using Pearson Chi-square. Because more than one AE may occur in an individual patient, the proportion of patients receiving AQ-13 with AEs will be compared with Coartem using Chi-square or the Fisher Exact test. The severity of AEs will be classified using the recent FDA Guidance for Healthy Adult and Adolescent Volunteers in Preventive Vaccine Trials [23], and the severity of AEs across the study arms will be compared using Chi-square. QT interval corrections for heart rate (QTc) will be made using both Bazett's and Fridericia's formulas [41-42]. Within-patient maximum changes from baseline will be assessed using the Wilcoxon test for paired observations. Between-group QT interval changes will be compared using ANOVA or Kruskal-Wallis.

HYPOTHESES BEING TESTED.

The primary hypothesis is that the efficacy of AQ-13 for uncomplicated *P. falciparum* malaria is similar to

that of Coartem - based on a non-inferiority margin of 15%. That is, that AQ-13 will produce a cure rate within 15% of the Coartem control (standard). The secondary hypothesis is that AQ-13 will have safety profiles in subjects with uncomplicated malaria comparable to those for AQ-13 in healthy volunteers [11].

EXPECTED OUTCOMES.

Our preliminary (previous) studies have shown that AQ-13 is:

- *active in vitro* against CQ-resistant and multi-resistant *P. falciparum* [8-9],
- *active in vivo* against CQ-resistant *P. falciparum* in the squirrel monkey model of human infection with CQ-resistant *P. falciparum* (enclosed Figures 1 and 2 in the Appendix), and
- *safe in human subjects* based on Phase 1 studies recently performed in New Orleans [11].

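### If the tested maximum QTc change is each patient's largest increase over several readings, the within-patient Wilcoxon test in Section 10.3 rejects too often with no drug effect; the term needs defining and should not be tested against zero

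*Combined protocol and SAP*

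**What the plan says.** The QTc analysis is set out in two sentences of Section 10.3. The within-arm part reads: "Within-patient maximum changes from baseline will be assessed using the Wilcoxon test for paired observations". The between-arm part follows: "Between-group QT interval changes will be compared using ANOVA or Kruskal-Wallis". Table 7 (Section 10.1) lists Wilcoxon and Friedman tests within individuals, and ANOVA and Kruskal-Wallis between groups. It does not mention a maximum.

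Section 7.1.2 gives the endpoint as "mean changes from the baseline pre-treatment QT (QTc) interval to the post-treatment QT (QTc) interval"; the synopsis and Section 3 are similar.

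Section 4 plans "7 Holter recordings at the times of screening (1 hour), during inpatient days 1-4 (24 hours each"), plus recordings at weeks 1 and 2. That makes one recording before dosing and six after. Section 6.2.2 describes the first: "subjects will have a 1 hour baseline Holter recording to exclude pre-existing arrhythmias". Section 6.5 describes the four inpatient recordings as "focusing on the time between 2 and 6 hours after dosing for maximal effects on the QT interval". The two late recordings last 2 hours in Section 4. They last 1 hour in Section 6.5 (week 1), in Section 6.6 ("there is a final 1 hour Holter recording at the 2 week follow-up visit") and in the footnote to Flow Chart 4 ("Holter recording for 1 hour at 1 and 2 week follow up visits").

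No section states which readings the maximum covers, whether it is the largest increase or the largest absolute change, or how many readings each patient contributes.

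**The concern.** A paired Wilcoxon test asks whether the per-patient change is centred on zero. The largest of several noisy differences from one baseline is not centred on zero, even when every post-dose reading has the same distribution as the baseline. Taking a maximum builds in a positive offset that grows with the number of readings. On that reading the null hypothesis is false by construction, and the p-value is not evidence of a drug effect.

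The largest increase is the ordinary meaning for a QTc safety summary, and the schedule supplies many post-dose readings against one short baseline. At stake is a secondary safety result: a significant within-patient QTc change could appear in either arm, or in both, with no drug effect.

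**Working it through.** **Figure to reproduce.** None. The documents give no SD, correlation, effect size, power or error rate for QTc.

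**Inputs from the documents.**
- Patients per arm: 33 randomised (Section 10.2), 28 evaluable (Section 5.1).
- One recording before dosing and six after (Section 4).
- The one-sided alpha of 0.025 in Section 10.3 is for the primary endpoint; none is stated for QTc.

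**Assumptions.** Two-sided 5%; normal errors; k = 3 or 6 post-dose readings with common SD σ and equal pairwise correlation ρ; baseline independent of them with SD rσ; no drug effect. The ms figures use σ = 10 ms.

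**Step 1: the built-in offset.** Let d_j = post_j − baseline. Then E[max d] = σ·√(1−ρ)·m_k, where m_k is the expected maximum of k independent standard normals (m_3 = 0.846, m_6 = 1.267).
- ρ = 0.5: 10 × 0.707 × 0.846 = 6.0 ms (k = 3); 10 × 0.707 × 1.267 = 9.0 ms (k = 6).
- ρ = 0.8: 10 × 0.447 × 0.846 = 3.8 ms (k = 3); 10 × 0.447 × 1.267 = 5.7 ms (k = 6).

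**Step 2: rejection rate.** With W the sum of the ranks of |y| over patients with y > 0, z = (W − n(n+1)/4) / √(n(n+1)(2n+1)/24). For n = 28 the null mean is 28×29/4 = 203 and the null SD is √(28×29×57/24) = √1928.5 = 43.9. Simulating max(d) with 4,000 trials per cell and no shift gave:

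| Baseline SD ratio r | k | ρ = 0 | ρ = 0.5 | ρ = 0.8 |
|---|---|---|---|---|
| 1 | 3 | 92% | 60% | 28% |
| 1 | 6 | 100% | 92% | 55% |
| 2 | 3 | 51% | 26% | 14% |
| 2 | 6 | 85% | 53% | 24% |
| 3 | 3 | 27% | 15% | 9% |
| 3 | 6 | 53% | 28% | 15% |

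The Monte Carlo standard error is at most √(0.25/4000) = 0.8 points, and repeat runs differ by about a point. At ρ = 0.95, r = 1, k = 3 the rate is about 10%. With n = 33 the rates are somewhat higher (r = 1, k = 3: 96%, 67%, 32%).

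**Step 3: other correlation structures.** If correlation decays between successive readings instead of being equal, then at n = 28 and r = 1 a correlation of 0.8 gives 52% (k = 4) and 80% (k = 6). A correlation of 0.95 gives 7% (k = 2), 17% (k = 4) and 29% (k = 6).

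**Step 4: quantities that keep the level.** Across all scenarios with no shift, a single pre-specified reading, the mean of the readings and the signed largest-absolute change reject 4-6% of the time. The between-arm test on the maxima rejects 4.6-5.0%, because both arms carry the same offset.

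**Step 5: a non-drug shift** (σ = 10 ms, n = 28, r = 1, ρ = 0.5). A common shift adds to the offset in Step 1.
- −5 ms, k = 3: 6.0 − 5 = +1.0 ms; 6% rejection.
- −5 ms, k = 6: 9.0 − 5 = +4.0 ms; 31%.
- −10 ms, k = 3: 6.0 − 10 = −4.0 ms; 33%, all towards shortening.
- −10 ms, k = 6: 9.0 − 10 = −1.0 ms; 7%.

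A within-arm test on the mean change has no offset to cancel the shift. With k = 3 and ρ = 0.5 to 0.8, a 5 ms shift in either direction makes it reject 43-48% of the time.

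**The case against.** **The term may be harmless.** Section 6.5 is the only hint, and it points to a window of peak effect. If the maximum is the change at one pre-specified peak time, or the signed largest-absolute change, the level is nominal. This stands: a reader might infer that the planned test is certainly invalid, and the documents do not go that far. What remains is that the ordinary reading fails, nothing rules it out, and the choice is left open.

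**The size rests on assumption.** This also stands. With highly correlated readings or a much noisier baseline, the inflation is small. The focus on 2-6 hours after dosing makes k = 6, which would include weeks 1 and 2, less well supported than a smaller k. The baseline is not fully settled either, since Section 14.3 also lists electrocardiograms at screening and enrolment.

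**Replacing the maximum by the mean does not rescue the within-arm test.** This is correct and shapes the fix. Any test against one pre-treatment hour during acute malaria also picks up recovery from malaria, and under a 5 ms fall with k = 3 the mean does worse than the maximum.

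**The endpoint wording.** A reader might infer that mean changes in Section 7.1.2 contradict maximum changes in Section 10.3. They need not: a mean across patients of each patient's maximum fits both. The match is unclear, not contradictory.

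**Reach.** QTc is one of six secondary endpoints. The randomised comparison is already planned and keeps its level. Neither the halting rules (Section 8.6) nor the discontinuation reasons (Section 6.8) use this p-value. All of this stands and limits the severity.

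**Conclusion.** The point holds conditionally. If the maximum is the largest increase over several post-dose readings, the within-patient Wilcoxon test in Section 10.3 does not keep its level when there is neither a drug effect nor a non-drug shift. At n = 28 with equal noise, equal correlation and k = 3 to 6, the false-positive rate is about 27-55% at correlation 0.8 and 60-93% at 0.5. It is about 10% at 0.95 with k = 3, and lower throughout with a noisier baseline. The number of readings, the noise ratio, the correlation and the two-sided 5% level are all assumptions.

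Two wider inferences are not supported. The error need not point to false prolongation, because a fall in QTc after acute malaria could cancel or reverse it. Nor is the whole QTc assessment compromised, because the between-arm comparison stays at about 5%. Severity is minor to moderate: a misleading p-value on a secondary safety endpoint, avoidable by wording.

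**What to change.** In Section 10.3:

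1. Do not test the within-patient maximum against zero. Define it as the largest increase over named recordings, name the baseline recording, and report it by arm descriptively.
2. Base QTc inference on the randomised AQ-13 minus Coartem difference in change from baseline, with a 95% CI, using the same pre-specified readings in both arms. State the days and which dose anchors the 2-6 hour window. Section 6.5 applies that window to days 1-4, while Flow Chart 4 shows study drug over three days, with AQ-13 once daily and Coartem twice daily.
3. Give each arm's mean change with a 95% CI as descriptive only, noting that baseline is a single hour during acute malaria.
4. Reconcile the 1-hour and 2-hour durations of the week 1 and week 2 recordings.

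The cost is wording; the recordings are the same. There are three statistical downsides, shown for σ = 10 ms, k = 3, n = 28, r = 1:

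- The between-arm contrast cannot show prolongation common to both drugs. With ρ = 0.5 to 0.8, a shared +10 ms is flagged 5-6% of the time between arms, against 95-97% by a within-arm test on the mean. This is why the within-arm estimates are kept.
- The between-arm interval is wider. For ρ from 0 to 0.8, the SD of a patient's mean change is 10·√(1 + (1+2ρ)/3) = 11.5 to 13.7 ms. The 95% half-width is 4.5-5.3 ms within an arm and 6.2-7.3 ms between arms.
- If the change is averaged over readings, a brief peak is diluted: +10 ms in one of three readings moves the mean by 10/3 = 3.3 ms. The descriptive maximum keeps such a peak visible.

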10 STATISTICAL CONSIDERATIONS

10.1 Study Outcome Measures

The primary, secondary and tertiary objectives (Section 3, above) and outcome measures (Section 8, above) in this study will be assessed statistically as outlined below (Table 7).

Table 7.

Statistical Assessment of Study Endpoints

COMPONENTS OF THE PRIMARY ENDPOINT

- Lack of recrudescence at 42 days
- < 25% of baseline asexual parasitemia on day 3
- Clearance of asexual parasitemia and fever by day 7

STATISTICAL TESTS

- Pearson χ^2 , Fisher Exact test
- Pearson χ^2 , Fisher Exact test
- Pearson χ^2 , Fisher Exact test

SECONDARY ENDPOINTS

- Adverse Events (AEs) Pearson χ^2 , Fisher Exact test
- Effects on the QT (QTc) Interval (within individuals) Wilcoxon, Friedman test
- Effects on the QT (QTc) Interval (between groups) ANOVA, Kruskal-Wallis test
- Pharmacokinetic Parameters for Parent Compounds (AUC_t, t_{1/2}, Vd/F, Cl/F, MRT) Mann-Whitney, Kruskal-Wallis
- Time to parasite Clearance, Recrudescence or Reinfection (between groups) Kaplan-Meier, Cox Hazard
- Time to fever clearance (between groups) Kaplan-Meier, Cox Hazard

TERTIARY ENDPOINTS

- Pharmacokinetics of metabolites as above
- Aminoquinoline (chloroquine) pruritus Fisher Exact test

AUC_t = total area under the curve; t_{1/2} = elimination half-life; Cl/F = oral clearance; Vd/F = oral apparent volume of distribution; MRT = mean residence time.

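### The between-arm QTc comparison omits baseline QTc as a covariate; adjusting for it is a cheap efficiency gain whose size the documents do not fix

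*Combined protocol and SAP*

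**What the plan says.** Section 10.3 describes the arm comparison in one sentence: "Between-group QT interval changes will be compared using ANOVA or Kruskal-Wallis". Table 7 in Section 10.1 repeats it: "Effects on the QT (QTc) Interval (between groups) ANOVA, Kruskal-Wallis test". Neither place names a covariate, and neither gives a rule for choosing between the two tests.

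The endpoint in Section 7.1.2 is "mean changes from the baseline pre-treatment QT (QTc) interval to the post-treatment QT (QTc) interval after treatment with AQ-13 or Coartem", so baseline already enters by subtraction. The within-patient analysis in Section 10.3 uses a different summary: "Within-patient maximum changes from baseline will be assessed using the Wilcoxon test for paired observations". Section 10.3 also corrects QT by both Bazett's and Fridericia's formulas and makes neither the main one.

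On data collection, Section 6.2.2 says: "Prior to treatment with AQ-13 or Coartem, subjects will have a 1 hour baseline Holter recording". It adds: "Randomization will be performed after the chemistry, hematology, eye and Holter recording results have been checked". A baseline recording should therefore exist for each randomized man and cannot be affected by treatment. After dosing starts, Section 6.5 says "continuous 24 hour Holter recordings will be performed on each of days 1-4", and 1-hour recordings follow at weeks 1 and 2.

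**The concern.** Subtracting baseline fixes its slope at 1. ANCOVA estimates the slope from the data. When the true slope is below 1, the change score over-corrects: an arm that starts with a higher QTc by chance tends to show a smaller rise, and this noise enters the arm difference. With about 30 men per arm and no stratification described in Section 10.4, such imbalances are to be expected.

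QTc is the planned cardiac safety comparison between the drugs and has no power calculation of its own. Section 10.3 names tests for it but no estimate with an interval. A non-significant ANOVA or Kruskal-Wallis result would not show how large a difference remains compatible with the data.

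**Working it through.** **The plan's own figures.** There are none for QTc: no SD, correlation, effect size or power. The number of men comes from the cure endpoint: 26 per arm before dropout, and 26 / 0.8 = 32.5, rounded up to 33 (Section 10.2, Table 8). Section 5.1 targets 28 evaluable per arm; Section 10.2 speaks of 26. I use 28 (N = 56); results at 26 and 33 are almost the same.

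**Assumptions.** Rho from 0.3 to 0.95; post-treatment to baseline SD ratio k from 0.8 to 1.4; SD 20 ms for results in milliseconds. None of these is in the documents.

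**Equal SDs (k = 1), variances in units of the squared SD.**
- Change score: 2(1 - rho).
- ANCOVA: 1 - rho².
- Ratio: (1 - rho²) / [2(1 - rho)] = (1 + rho)/2.
- Cost of estimating the slope: factor (N - 3)/(N - 4) = 53/52 = 1.019, or about 1.9%, with 53 instead of 54 degrees of freedom for t.

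The 95% half-widths at SD 20 ms are:
- change score: t(54) × 20 × √[2(1 - rho)] × √(2/28);
- ANCOVA: t(53) × 20 × √(1 - rho²) × √[(2/28)(53/52)].

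| rho | (1 + rho)/2 | net variance ratio | change score, ms | ANCOVA, ms | interval narrower by |
|---|---|---|---|---|---|
| 0.3 | 0.650 | 0.662 | 12.68 | 10.33 | 18.6% |
| 0.5 | 0.750 | 0.764 | 10.72 | 9.37 | 12.5% |
| 0.7 | 0.850 | 0.866 | 8.30 | 7.73 | 6.9% |
| 0.8 | 0.900 | 0.917 | 6.78 | 6.49 | 4.2% |
| 0.9 | 0.950 | 0.968 | 4.79 | 4.72 | 1.6% |
| 0.95 | 0.975 | 0.994 | 3.39 | 3.38 | 0.3% |

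The variances break even at rho = 2 × 52/53 - 1 = 0.96. In 20,000 simulated trials per rho, the ANCOVA interval was the narrower one in 99% of trials at rho 0.5, 83% at 0.8, 62% at 0.9 and 44% at 0.95.

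**Unequal SDs.** Before the slope cost, the ratio is k²(1 - rho²) / (1 + k² - 2 rho k).
- k = 0.8, rho = 0.8: 0.64 × 0.36 / (1 + 0.64 - 1.28) = 0.2304/0.36 = 0.64, a larger gain.
- k = 1.25, rho = 0.8: 1.5625 × 0.36 / (1 + 1.5625 - 2) = 0.5625/0.5625 = 1.00, no gain. This happens wherever rho × k = 1, because the true slope is then 1.

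**Chance imbalance.** With SD 20 ms, the standard error of the baseline difference is 20 × √(2/28) = 5.3 ms. For equal SDs, an imbalance of that size moves the change-score contrast by (1 - rho) × 5.3 ms: 2.7 ms at rho 0.5, 1.6 ms at 0.7 and 0.5 ms at 0.9.

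These ratios are against ANOVA on changes. They do not measure the gain over Kruskal-Wallis.

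**The case against.** The strongest reply is that the planned analysis is sound. It already uses baseline through the change score, and under randomization that contrast is unbiased on average. QTc is a secondary endpoint with no margin or threshold, and the halting rules in Section 8.6 rest on graded adverse events and treatment failures. All of this stands, and it limits the point to efficiency.

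The second reply is that the gain cannot be shown to be large. A reader might infer that a 1-hour baseline taken in acute malaria must be noisy and only moderately correlated with later values. Taking rho from 0.4 to 0.7 would then make adjustment worth 18% to 43% more patients (1/0.85 and 1/0.70). The documents do not support this:
- They report no correlation and no SD, and high values of rho are no worse documented than moderate ones.
- An hour of Holter data contains many beats, so its length alone does not show that the summary is noisy.
- Section 14.3 lists electrocardiograms as well as Holter recordings, and no section says which tracing supplies baseline QTc.
- The 18% to 43% figure also needs equal SDs, which should not be taken for granted when 1-hour and 24-hour recordings are compared.

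The third reply is that ANCOVA cannot be run until its outcome is defined. The plan mixes mean and maximum change, uses two correction formulas, and leaves open which of days 1-4, the period 2 to 6 hours after dosing (Section 6.5), or weeks 1 and 2 is meant. This also stands, and the fix must settle it. It does not make adjustment for baseline wrong.

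**Conclusion.** The point holds as an efficiency improvement on a secondary safety endpoint. The plan compares unadjusted changes although a pre-randomization baseline should be available for every man. At 28 per arm with equal SDs, the 95% interval would narrow by about 19% at rho 0.3, 12.5% at 0.5, 7% at 0.7, 4% at 0.8, 2% at 0.9 and almost nothing at 0.95. With unequal SDs the gain can be larger, or nil where rho × k = 1. All of this rests on assumed values of rho and k.

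Two stronger readings should be avoided. One is that adjustment is certain to give a clearly tighter answer at no cost: the size is unknown and there is a small price. The other is that the planned test is biased or invalid: it is neither. No primary conclusion and no sample size depends on this point.

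**What to change.** In Section 10.3 and Table 7, replace the between-group ANOVA or Kruskal-Wallis with the following:
- Name one post-treatment QTc summary (which recordings, which time window, mean or maximum) and bring Sections 7.1.2 and 10.3 into line with it.
- Name one heart-rate correction as the main one and report the other as secondary.
- State which pre-treatment recording supplies baseline QTc.
- Fit ANCOVA with that post-treatment summary as outcome, treatment as factor and baseline QTc as covariate. Report the adjusted AQ-13 minus Coartem difference with its 95% confidence interval.
- Pre-specify a rank-based ANCOVA as a sensitivity analysis, always reported, so that the choice of method does not depend on how the data look.

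The cost is a wording change and one degree of freedom, about 1.9% in variance at N = 56. It needs no new data or visits. The wording should be settled before unblinded QTc data are seen.
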